8.4. Method of Treatment Assignment

Each patient who signs the ICF will be assigned a patient number and tracked centrally.

Eligible patients will be enrolled sequentially as confirmed and tracked by the sponsor.

Details on treatment assignment can be found in the Interactive Web Response System (IWRS) manual.

8.5. Blinding

This is a single arm study. Blinding is not applicable.

8.6. Treatment Logistics and Accountability

8.6.1. Packaging, Labeling, and Storage

8.6.1.1. Cemiplimab

Study drug will display the product lot number on the label.

Study drug will be stored at the site at a temperature of 2°C to 8°C; storage instructions will be provided in the pharmacy manual.

8.6.1.2. ISA101b

ISA101b is provided in 2 vials, HPV-DP-5P containing 5 peptides and HPV-DP-7P containing 7 peptides. Bulk preparation, sterile filtration, filling, and lyophilization have been developed for each product.

Lyophilized powder of the 2 drug products is stored in glass vials in the dark at -20°C.

Before SC injection, the peptide compositions of each of the 2 drug products will be reconstituted in Reconstitution Solution (containing Water For Injection, Ethanol, Propylene Glycol, Citric acid and Macrogolglycerol Ricinoleate) and mixed with Montanide.

8.6.2. Supply and Disposition of Treatments

8.6.2.1. Cemiplimab

Cemiplimab will be shipped at a temperature of 2°C to 8°C to the investigator or designee at regular intervals or as needed during the study. At specified time points during the study (eg, interim site monitoring visits), at the site close-out visit, and following drug reconciliation and documentation by the site monitor, all opened and unopened study drug will be destroyed at the site or returned to the sponsor or designee.

8.6.2.2. ISA101b

The Sponsor will provide ISA101b to the study sites.

The maximum recommended hold time between ISA101b vaccine preparation and administration is 2 hours. Instructions for vaccine preparation and administration are given in the Pharmacy Manual. The ISA101b vaccine consists of 2 separate injections and is administered in 2 different limbs. It is recommended to administer the vaccine in 2 different limbs and rotate injection sites between administrations, eg, first ISA101b vaccination in the upper-legs, second ISA101b vaccination in the upper-arms and third ISA101b vaccination in the upper-legs.

Additional information regarding ISA101b is provided in the ISA101b Investigator's Brochure.

8.6.3. Treatment Accountability

All drug accountability records must be kept current.

The investigator must be able to account for all opened and unopened study drug. These records should contain the dates, quantity, and study medication

- Dispensed to each patient
- Returned from each patient (if applicable), and
- Disposed of at the site or returned to the sponsor or designee.

All accountability records must be made available for inspection by the sponsor and regulatory agency inspectors; photocopies must be provided to the sponsor at the conclusion of the study.

8.6.4. Treatment Compliance

All drug compliance records must be kept current and made available for inspection by the sponsor and regulatory agency inspectors.

8.7. Concomitant Medications

Any procedure performed or treatment administered (prescription medications and over-the-counter preparations) from the time of informed consent until 90 days after the last study treatment or start of another systemic anticancer therapy, whichever comes first, will be considered

concomitant treatment. This includes medications and other therapies for which administration started 30 days before the first dose of the study drug and will continue during the study, as well as any therapies started in the follow-up period to treat a study-drug-related AE. All concomitant treatments must be recorded in the study eCRF with the generic name, dose, dose unit, frequency, indication, and start/stop date, as appropriate.

8.7.1. Prohibited Medications

While participating in this study, a patient may not receive any standard or investigational agent for treatment of a tumor other than cemiplimab as monotherapy or in combination with ISA101b, per the study's specified dosing regimens.

- After communication with the sponsor, focal palliative treatment (eg, radiation) is allowed under the following circumstances:
 - For local control of a tumor once a patient has completed 24 weeks of study treatment.
 - For pain management at sites of bone disease or lesions in the brain (as long as the lesions are not followed for treatment response evaluation).
- Patients using immunosuppressive doses (>10 mg per day of prednisone or equivalent) of systemic corticosteroids other than for corticosteroid replacement will not be eligible for the study. It is recommended that patients do not receive systemic corticosteroids such as hydrocortisone, prednisone, prednisolone (Solu-Medrol®), or dexamethasone (Decadron®) at any time throughout the study except in the case of a life-threatening illness and/or to treat an imAE.
- It is recommended that patients do not receive other immunosuppressive medications at any time throughout the study except in the case of a life-threatening emergency and/or to treat and imAE or IRR. Examples of immunosuppressives that may be used for treatment of imAEs are mentioned in [Appendix 2](#). Investigators are allowed to treat adverse events requiring immunosuppressive medication using their institutional standard, which may involve medications not specifically mentioned in the protocol.
- Prophylactic or therapeutic anticoagulation therapy is allowed after discussion with study sponsor as gastrointestinal adverse events are common with immune checkpoint inhibitors. Patients on anticoagulants have to be monitored closely.
- Patients are not allowed to undergo surgical resection of the primary tumor site.

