9.1.2. End of Treatment Visit

All patients will attend an end of treatment visit 30 days after their last dose of study drug.

Patients who are withdrawn from the study before the primary endpoint visit (cycle 4 day 43) will be asked to return to the clinic once for an end of treatment visit consisting of the assessments described in [Table 2](#).

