11.4.3. Efficacy Analyses

In order to describe ORR, the interim data cutoff for efficacy analysis will be after the 53rd patient enrolled has had an opportunity for 4 tumor assessments.

The final data cutoff for efficacy analysis will be when the last patient enrolled has had the opportunity for 4 tumor assessments.

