1.2.1. Special Considerations

Bone lesions:

- Bone scan, PET scan or plain films are not considered adequate imaging techniques to measure bone lesions. However, these techniques can be used to confirm the presence or disappearance of bone lesions.
- Lytic bone lesions or mixed lytic-blastic lesions, with identifiable soft tissue components, that can be evaluated by cross sectional imaging techniques such as CT

or MRI can be considered measurable lesions if the soft tissue component meets the definition of measurability described above.

- Blastic bone lesions are non-measurable.

Cystic lesions:

Cystic lesions that meet the criteria for radiographically defined simple cysts should not be considered malignant lesions (neither measurable nor nonmeasurable) since they are, by definition, simple cysts. “Cystic lesions” thought to represent cystic metastases can be considered measurable lesions, if they meet the definition of measurability described above. However, if non-cystic lesions are present in the same patient, these are preferred for selection as target lesions.

Lesions with prior local treatment:

- Tumor lesions situated in a previously irradiated area, or in an area subjected to other locoregional therapy, are usually not considered measurable unless there has been demonstrated progression in the lesion.

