1.5.1. Evaluation of Target Lesions

- **Complete Response (CR):** Disappearance of all target lesions. Any pathological lymph nodes (whether target or non-target) must have reduction in short axis to <10 mm (<1 cm).
- **Partial Response (PR):** At least a 30% decrease in the sum of the diameters of target lesions, taking as reference the baseline sum diameters.
- **Progressive Disease (PD):** At least a 20% increase in the sum of the diameters of target lesions, taking as reference the smallest sum on study (this includes the baseline sum if that is the smallest on study). In addition to the relative increase of 20%, the sum must also demonstrate an absolute increase of at least 5 mm (0.5 cm). (**Note:** the appearance of one or more new lesions is also considered progression).
- **Stable Disease:** Neither sufficient shrinkage to qualify for PR nor sufficient increase to qualify for progressive disease, taking as reference the smallest sum diameters while on study.

Special notes on the assessment of target lesions:

- Lymph nodes: Lymph nodes identified as target lesions should always have the actual short axis measurement recorded and should be measured in the same anatomical plane as the baseline examination, even if the nodes regress to below 10 mm on study. This means that when lymph nodes are included as target lesions, the ‘sum’ of lesions may not be zero even if complete response criteria are met, since a normal lymph node is defined as having a short axis of <10 mm.
- Target lesions that become ‘too small to measure’: All lesions (nodal and non-nodal) recorded at baseline should have their actual measurements recorded at each subsequent evaluation, even when very small (eg, 2 mm). If the radiologist is able to provide an actual measure, that should be recorded, even if it is below 5 mm. However,

when such a lesion becomes difficult to assign an exact measure to then: (i) if it is the opinion of the radiologist that the lesion has likely disappeared, the measurement should be recorded as 0 mm. (ii) if the lesion is believed to be present and is faintly seen but too small to measure, a default value of 5 mm should be assigned (note: in case of a lymph node believed to be present and faintly seen but too small to measure, a default value of 5 mm should be assigned in this circumstance as well). This default value is derived from the 5 mm CT slice thickness (but should not be changed with varying CT slice thickness).

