1.7. Evaluation of Best Overall Response

The best overall response is the best response recorded from the start of the treatment until the end of treatment taking into account any requirement for confirmation. The patient's best response assignment will depend on the findings of both target and non-target disease and will also take into consideration the appearance of new lesions.

Revised Response Evaluation Criteria in Solid Tumors (RECIST) Version 1.1 ([Eisenhauer, 2009](#)) is summarized in the table below.

Response According to Revised Response Evaluation Criteria in Solid Tumors (Version 1.1) in Patients with Target (and Non-Target) Lesions When Confirmation is Required

Target Lesions	Non-target Lesions	New Lesions	Overall Response	Best Overall Response when Confirmation is Required
CR	CR	No	CR	≥ 4 weeks confirmation
CR	Non-CR/non-PD*	No	PR	
CR	Not evaluated	No	PR	
PR	Non-CR/non-PD/not all evaluated	No	PR	
SD	Non-CR/non-PD/not all evaluated	No	SD	Documented at least once ≥ 4 weeks from baseline
Not all evaluated	Non-PD	No	NE	
PD	Any	Yes or no	PD	No prior SD, PR, or CR
Any	PD**	Yes or no	PD**	
Any	Any	Yes	PD	

Abbreviations: CR=complete response; PD=progressive disease; PR=partial response; SD=stable disease; NE=not evaluable.

*For non-target disease, 'non-CR/non-PD' is preferred over 'SD' since SD is increasingly used as endpoint for assessment of efficacy in some trials, so to assign this category when no lesions can be measured is not advised.

**In exceptional circumstances, unequivocal progression in non-target lesions may be accepted as PD.

Note: Patients with a global deterioration of health status requiring discontinuation of treatment without objective evidence of disease progression at that time should be reported as "symptomatic deterioration." Every effort should be made to document the objective progression even after discontinuation of treatment.

Best Overall Response When Confirmation of CR and PR are Required

Overall Response, First Time Point	Overall Response, Subsequent Time Point	Best Overall Response
CR	CR	CR
CR	PR	SD, PD, or PR*
CR	SD	SD if minimum criteria for SD duration met, otherwise PD
CR	PD	SD if minimum criteria for SD duration met, otherwise PD
CR	NE	SD if minimum criteria for SD duration met, otherwise NE
PR	CR	PR
PR	PR	PR
PR	SD	SD
PR	PD	SD if minimum criteria for SD duration met, otherwise PD
PR	NE	SD if minimum criteria for SD duration met, otherwise NE
NE	NE	NE

Adapted from ([Eisenhauer, 2009](#))

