4.4. Efficacy Variable

4.4.1. Primary Efficacy Variable

Overall response is determined by RECIST version 1.1 ([Eisenhauer, 2009](#)).

Best overall response (BOR) is determined once all the overall response data for the patient are known. The best overall response is the best response recorded during the study:

- Best overall response of CR or PR must be confirmed by consecutive evaluations of overall response of CR or PR at time points at least 4 weeks apart.
- Best overall response of SD must have met the response SD criteria at least once \geq 42 days (7 weeks - 7 days) after start of study treatment. Best overall response of (early) PD does not require confirmation using the RECIST.
- The best overall response for patients who do not have any post-baseline tumor assessment will be not evaluable (NE). Patients with best overall response of NE will be considered as not reaching an objective response of CR or PR.

Objective response rate (ORR) is determined by the proportion of patients with best overall response of CR or PR in the FAS.

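### Radiation to a target lesion is permitted after 24 weeks and best overall response has no cut-off there, so radiation shrinkage could count towards a confirmed PR in ORR (minor)

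*Protocol*

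**What the plan says.** **Radiation on study.** Protocol 8.7.1 allows focal palliative treatment such as radiation after communication with the sponsor, in two situations. One is "For local control of a tumor once a patient has completed 24 weeks of study treatment". The other is pain management at bone disease or brain lesions, and only that one carries a condition: "as long as the lesions are not followed for treatment response evaluation". Section 8.7.1 states no approval step and no lesion criterion for the local-control case.

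**Response window.** SAP 4.4.1 states: "The best overall response is the best response recorded during the study". Protocol Appendix 3, section 1.7, defines it as "the best response recorded from the start of the treatment until the end of treatment". Radiation given while the patient stays on study drug falls inside both windows. A BOR of CR or PR needs consecutive evaluations at least 4 weeks apart, and ORR is the share of the FAS with such a BOR. SAP 4.4.2 has a new-anti-cancer-therapy rule for DOR and PFS; SAP 4.4.1 has none for BOR.

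**Response criterion.** PR is "At least a 30% decrease in the sum of the diameters of target lesions" relative to baseline (Appendix 3, section 1.5.1), whatever caused the decrease.

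**Nearest text on irradiated lesions.** Appendix 3, section 1.2.1, says that lesions with prior local treatment "are usually not considered measurable unless there has been demonstrated progression in the lesion". It belongs to the classification of disease at baseline. SAP 6.2 makes patients deemed NE non-responders, but does not make a target irradiated on study non-evaluable.

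**Cutoff.** Protocol 11.4.3 sets the final efficacy cutoff "when the last patient enrolled has had the opportunity for 4 tumor assessments". Patients enrolled earlier therefore contribute scans beyond their fourth.

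**The concern.** ORR is meant to estimate the activity of cemiplimab + ISA101b. Take a patient with stable disease at week 25 who then has a target lesion irradiated for local control. She stays on study drug, keeps her scan schedule and, if the irradiated lesion is still measured, may cross the 30% threshold because of the radiation. As written, the plan would count her as a responder.

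The pain bullet shows that the authors saw the need to keep radiation away from response lesions; the local-control bullet omits the same protection. There is no control arm in which the same artefact would appear, the primary endpoint is investigator-assessed, and independent review of scans is at the sponsor's discretion (Protocol 9.2.2.1). The confidence interval does not reflect this kind of misclassification.

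**Working it through.** **1. The plan's own precision.** Inputs: N = 105 and a normal-approximation 95% interval (SAP 2.2 and 5.7.1). Half-width = 1.96 × √(p(1 − p)/105).
- 21/105 = 20.0%: half-width 7.65 points (stated 7.7).
- 36/105 = 34.3%: half-width 9.08 points (stated 9.1).

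The stated range reproduces.

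**2. Scan days.** Cycle 1 lasts 7 weeks, cycles 2 to 4 last 6 weeks each, later cycles 9 weeks, with a scan at the end of each. On treatment, scans fall on days 50, 92, 134, 176, 239 and 302, that is, weeks 7, 13, 19, 25, 34 and 43.

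**3. When radiation becomes possible.** Counted from day 1, 24 weeks are complete on day 169 (24 × 7 + 1).
- Scans 1 to 3 (last on day 134) come before this.
- Scan 4 is due 176 − 169 = 7 days after it, or 14 days with the +7-day imaging window.

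So scans 1 to 3 cannot be affected and scan 4 barely can. Protocol 9.1.2 calls the scan 4 visit (cycle 4 day 43) the primary endpoint visit, but BOR does not stop there.

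**4. Routes to a confirmed PR.**
- SD at week 25, radiation to a target, then PR at weeks 34 and 43.
- Unconfirmed PR at week 25, radiation to a target, then PR at week 34.

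The later scheduled scans are 63 days apart, so the 4-week confirmation interval is met.

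**5. Is there follow-up for this before cutoff?** Assume even accrual over 52 weeks (Protocol 6.1 gives approximately 12 months) and cutoff at the last patient's week 25. Share with at least f weeks of follow-up = (52 + 25 − f)/52.
- f = 34: 43/52 = 82.7%, about 87 of 105.
- f = 43: 34/52 = 65.4%, about 69 of 105.

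With 78 weeks of accrual the shares would be 88.5% and 76.9%. All are calendar shares of everyone enrolled, before attrition.

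**6. Size.** Each patient counted this way adds 1/105 = 0.95 points.
- One patient: 24/105 = 22.9% (14.8, 30.9) becomes 25/105 = 23.8% (15.7, 32.0).
- Three patients: 27/105 = 25.7% (17.4, 34.1), a shift of 3/105 = 2.86 points.
- Eight patients: 8/105 = 7.62 points, about the smallest half-width (7.65).

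The documents give no radiation frequency, so the range of one to three is an assumption.

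**The case against.** **Few patients can follow this route.** The patient must be on study drug at 24 weeks without progression or a confirmed response, need palliative local treatment, have it aimed at a target lesion, and then hold a 30% fall in the sum of up to five targets on two evaluations before cutoff. With five targets of equal diameter, losing one completely lowers the sum by only 1/5 = 20%; with three it is 1/3 = 33%. This stands, and it is why the expected effect is small.

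**The answer may lie elsewhere.** Appendix 3 is an excerpt that refers to the full RECIST publication, and Protocol 9.2.2.1 refers to a Site Imaging Manual. Neither was available. A convention for targets irradiated on study could be there. The point is therefore shown for the protocol and SAP only, although a rule that fixes the primary endpoint belongs in the SAP.

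**A reader might infer that the error can only favour the regimen.** The documents do not support that. It holds only if the irradiated target is still scored as evaluable. If sites treat it as not evaluated, the section 1.7 tables give NE at that visit, and a PR followed by NE becomes SD (or NE if the minimum SD duration is not met). A genuine responder would then be lost and ORR would fall.

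**A reader might also extend the point to DOR and PFS.** SAP 4.4.2 already has a new-therapy rule for both. Whether permitted palliative radiation triggers it is an unstated detail, not a demonstrated error.

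**Conclusion.** The gap is real and minor. Followed as written, the protocol and SAP allow shrinkage of an irradiated target after about week 25 to count towards a confirmed PR, provided the lesion is still measured. The size is 0.95 ORR points per patient. One to three patients, an assumed number, would shift the estimate by 0.95 to 2.9 points, well inside the planned half-width.

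Two stronger readings should be resisted. First, the 83% and 65% shares might be taken as ceilings on exposure. They are illustrations: accrual is only approximate, the primary analysis requires at least four assessments rather than exactly four, scans have ±7-day windows, and end-of-treatment or unscheduled scans could supply a confirmation. Nor do they measure the number at risk, which is far smaller and not given. Second, one might conclude that ORR will be materially inflated or a decision changed. The documents give no frequency to support the former, and Protocol 11.1 states that there is no formal hypothesis, so no formal decision depends on the figure.

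**What to change.** Add one sentence to SAP 4.4.1: only assessments on or before the date of the first local therapy to a target lesion count for reaching or confirming CR or PR. Add a flag on the tumor CRF for target lesions irradiated on study. Concomitant treatments and their dates are already recorded in the eCRF (Protocol 8.7), and SAP section 1 allows revision before database lock. Patient care does not change.

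The cost is statistical. A true PR first seen before radiation, with its confirming scan afterwards, would not be counted, nor would a late response first appearing after radiation. ORR may therefore be slightly lower. For a single-arm estimate that is an acceptable price, and fixing the rule in advance avoids deciding case by case once responses are known.

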8.7.2. Permitted Medications

While participating in this study, a patient may receive medications or therapies other than study drug under the following conditions:

- Physiologic replacement doses of systemic corticosteroids are permitted, even if >10 mg/day prednisone equivalents.

- A brief course of corticosteroids for prophylaxis (eg, contrast dye allergy) or for treatment of non-autoimmune conditions (eg, delayed-type hypersensitivity reaction caused by contact allergen) is permitted.
- Gonadotropin-releasing hormone agonist therapy (eg, for prostate cancer) may be continued and is not prohibited.
- Hormone-replacement therapy is allowed.
- Inhaled, topical, ophthalmologic, or intranasal steroids are allowed.
- Treatments for bone metastases (bisphosphonates, denosumab) are allowed.
- Any other medication which is considered necessary for the patient's welfare, and which is not expected to interfere with the evaluation of the study drug, may be given at the discretion of the investigator.

COVID-19 Vaccination During the Study

COVID-19 vaccination may be administered to patients enrolled in R2810-ONC-ISA-1981 in accordance with local regulatory guidance. Currently, there is limited data on safety and efficacy interactions between approved COVID-19 vaccines and cemiplimab and/or ISA101b.

It is recommended for patients to complete COVID-19 vaccination at least 14 days prior to receiving the first dose of ISA101b or to delay COVID-19 vaccination until at least 14 days after the final dose of ISA101b.

It is recommended to use different limbs for the administration of a COVID-19 vaccine and contiguous ISA101b vaccine. It is recommended not to receive a COVID-19 vaccine if the patient has a known allergy to the COVID-19 vaccine or one of its components.

There should be an individual risk/benefit analysis for each patient when receiving COVID-19 vaccination while enrolled in R2810-ONC-ISA-1981.

